## Randomization Procedure

Participants were randomized to a gamified (*mLife+points*) or non-gamified (*mLife*) version of the *mLife* mobile weight loss intervention where provision of social support was incentivized by providing points for engaging in social support activities (for the *mLife+points* group) or not receiving points for social support activities (*mLife* group).

Participants are randomly assigned once 50% of the baseline assessments are completed (either the baseline survey or the three dietary recalls). A computerized blocks system, stratified by race (Black, Other) and sex, is used to ensure equal distribution among groups within each cohort. [name] generates a random list of two groups (0s = Standard, 1s = *mLife*) in blocks of 10 or 4. Separate blocks are created for women and men, as well as white and non-white participants, this results in 15 blocks of 10 for non-white women, 30 blocks of 10 for white women, 3 blocks of 5 for non-white men, and 5 blocks of 4 for white men.

As participants complete 50% of the assessment, a blind staff member uses the demographic data report from RedCap to identify each participant by gender and race and add the participant's ID number to the next available spot on the blocks. The group allocation will then be recorded in the RedCap project under the randomization form (randomization event). Participants will not be informed of their group assignment but will be provided with their choice of meeting times and days for the training session. On the day of randomization, participants will be contacted and asked to select the time and date they plan to attend. The group allocation will be revealed at the first group meeting, after all baseline assessments have been completed. Since the training sessions are scheduled by group, the randomization process must occur before inviting participants to the training meeting.

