## Study Intervention

The intervention design promoted weight loss and weight-loss maintenance by focusing on diet and PA behaviors and facilitating social support, grounded in theoretical perspectives such as supportive action, appraisal, and relationships, as well social support provision and receipt.

The mLife intervention consisted of 5 main components: daily tracking of 1) diet, 2) PA, and 3) body weight; 4) podcasts and tips of the day; and 5) gamification of social support activities. As mentioned above, participants were provided a Fitbit watch and scale for PA and body weight tracking, with all intervention components implemented remotely through the mLife app (cohort 2 tracked diet outside of the app). Both groups will be instructed to follow the same

dietary (reduced energy diet) and PA recommendations (progressed up to a goal of 150 minutes of moderate or 75 minutes of vigorous activity/week). These recommendations will be provided via handout at the orientation and reinforced in the podcasts. The figure below displays images of the mLife app components.

mLife intervention components delivered via the mLife app:  
 a. diet, physical activity (PA), and weight tracking; b. leaderboard and points tracker; c. tips of the day; d. newsfeed; e. social support requests

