## App Development and Use

A progressive web application, incorporating improved features from the pilot Social POD app, delivered the mLife weight loss program. It integrated the NutritionIX Database via API for diet logging. For cohort 2, Participants used FitBit devices to track activity and weight, and the API displayed Fitbit data.

Based on Cohort 1 feedback, two adjustments were made for Cohort 2. Participants were initially limited to one response to peer support requests, but this hindered social interactions, so unlimited responses were allowed. The in-app graph displayed only “active minutes” per day, but the FitBit app emphasized “active zone minutes,” so the mLife app adjusted to display both.

Cohort 2 also made an adjustment based on Cohort 1 feedback. Participants expressed dissatisfaction with the in-app diet tracking feature’s lack of recipe building and barcode scanning. So, Cohort 2 logged their diet in the Fitbit app, and the data was synchronized to the mLife app.

Participants and staff member accessed the mLife application from the study’s website, under the login menu: <https://mlifestudy.org/study/guest/login> Participants access their account using the Email provided during the orientation, contact information form in RedCap project.

IT team assist with any account issues or data display concerns through the help request RedCap project, as detailed under retention strategies.

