## Social support activities and gamification

The mLife app offered eight social support activities to engage users and test gamification. It automatically posted newsfeed when users logged meals, exercised, tracked weight, or listened to podcasts. Users could “like” posts and request support from peers by commenting or asking questions. Peers could comment and respond to support requests, and users received notifications when peers offered support. Refer to the graph below that shows the gamified social actions within the application id and point value for the leaderboard.

[figure not shown]

Id	Name	Point Value
3	Respond to a support request*	1
4	Outreach	1
5	Thank for thumbs up/Comment*	1
6	Request support	1
7	Thumbs up logged weight	1
8	Thumbs up logged diet	1
9	Thumbs up logged physical activity	1
10	THUMBS UP READ TIP OF THE DAY OR LISTENED TO A... 	1
12	Reply to a Comment	0

Participants are also prompted to send supportive messages to inactive peers. When inactive for more than 24 hours, an outreach request is posted in the newsfeed: “(username) hasn’t been active for more than a day. Please send them an encouraging message to return.” Participants can choose a pre-written message or create a custom message and send it via text. Pre-written messages are created using Social Cognitive Theory to target social support, self-efficacy, and outcome expectations regarding self-monitoring behavior. Once an outreach message is sent, the request is closed.

Participants earn up to 8 points per day for social support interactions. They can provide support as many times as desired, with a maximum of 1 point per activity. The mLife+Points group views the 8 activities, their daily points, and an overall leaderboard that resets monthly to boost motivation. The mLife group is unable to see the points earned; they have daily checklists. However, the mLife app calculates points for objective comparison between groups.

Posting a “request for support” comment or question in the app’s newsfeed allows mLife peers to comment and respond. Initially, participants could only post one response to peer requests to control moderation, but this limited social interactions, so unlimited responses were allowed at the 8 weeks data inspection. See the comment replies example graph below.

All participants' social interactions are posted in the newsfeed.

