### ***Aims 1 and 2***

We are powering our study to detect differences in weight loss at one year between those randomized to mLife+points and mLife groups (Aim 1) and differences in social support provision and receipt at one year between groups (Aim 2). For Aim 1 power, we used an F-test on the interaction between time (two levels) and treatment arm (two levels) in a two-way ANOVA with repeated measurements. We assumed **conservatively** a small effect size (Cohen's  $d = 0.1$ ).

Moreover, we used our NETworks pilot work, which collected weight loss outcomes at one year, to determine the intra-cluster correlation (ICC) which is the correlation of weight between times within individuals. The pilot study estimate of the ICC was 0.9 but we judged that this estimate may be too optimistic and lead to an inadequately low sample size (see Table 5). Therefore, we used a more **conservative** ICC = 0.7. In summary, we calculated that to achieve 95% power (alpha = 0.05) for Aim 1 assuming a small effect size (Cohen's  $d = 0.1$ ) and ICC equal to 0.7, we need a sample size equal to 200. Further, we assumed an attrition rate of 15-20% and increased the sample size to 240. Thus, we aim to recruit a total of 240 participants (~120 per cohort), with the initial randomization assigning 120 to mLife+points and 120 to mLife. This sample size will also give us abundant power for the study in Aim 2. Based on our Social POD pilot work, we are powering Aim 2 from both differences in overall app usage (Social POD  $50.7 \pm 25.0$  days and standard  $34.4 \pm 25.8$  days out of a possible 84 days) and points earned (representing social support provision). Social POD pilot participants earned a mean of  $202 \pm 105$  points/participant. We are assuming a difference of 50 points between groups with a SD of 105. Therefore, with the sample size chosen for Aim 1, our

power for Aim 2 will be 99% for app usage and 95% for points earned.

The sample size for our study has been chosen to ensure sufficient statistical power to detect differences in weight loss at one year after baseline between those randomized to mLife+points and mLife groups (Aim 1) and differences in social support provision and receipt and at one year between groups (Aim 2).

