### **III. Below describes our plans for interim and final analyses and methods for handling missing data:**

#### ***Aims 1 and 2***

Data from all study measures will undergo initial data cleaning to identify potential outliers, determine distributions of variables, assess normality, and enumerate loss to follow-up and other missing data. Descriptive statistics at baseline will be compared between treatment groups to evaluate the success of randomization. ***Analyzing changes in weight between groups at year one***

***(Primary Aims 1):*** For Aim 1, the two levels of the treatment effect will be assignment to SocialPOD+points vs. SocialPOD-points, and the entire study sample will be included. Primary Aim 1 will be addressed using a repeated-measures mixed model with maximum likelihood estimation as provided by PROC MIXED in the SAS® system. Under the assumption that missing data are missing at random, mixed models provide unbiased estimates. These will be adjusted using robust computation of standard errors if non-normality is detected. These models will be estimated applying an intent-to-treat principle. Models for each primary aim are of the same form, with the difference of the groups being compared. Models will examine weight at baseline and at 12 months with a two-level time effect, two-level treatment effect, and two-way interaction between time and treatment. The repeated-measures model will contain time, treatment, time-by-treatment interactions, and any covariates associated with weight loss. Models will be adjusted for changes in PA (via

accelerometers). If the time-by-treatment interaction in a model is significant at the 0.05 level, this will be interpreted as a significant weight-loss effect for one treatment relative to the other.

**Analyzing differences in social support provision and receipt between groups (Aim 2):** For Aim 2, the model will regress support provided (total points earned) and social support received (mean of ratings of support provided to the individual over the 12 months) on treatment group, adjusted for the same covariates used in Aim 1.

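### Randomisation is balanced within two cohorts that used partly different app versions, but neither the Aim 1 nor the Aim 2 model pre-specifies cohort

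*Combined protocol and SAP*

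**What the plan says.** All references are to the combined protocol and SAP.

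**Design.** Overview of assessments describes two cohorts of 120, staggered by 12 months. Randomization Procedure describes a blocked allocation that "is used to ensure equal distribution among groups within each cohort".

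**App versions.** App Development and Use states: "Based on Cohort 1 feedback, two adjustments were made for Cohort 2". The two are removal of the limit of one response per peer support request and display of a second activity measure. The same section adds that Cohort 2 logged diet in the Fitbit app, with the data synchronised to mLife. Study Intervention agrees: "cohort 2 tracked diet outside of the app". On the response limit, however, Social support activities and gamification says that the restriction hampered interaction, "so unlimited responses were allowed at the 8 weeks data inspection". It names no cohort.

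**Models.** Analysis Plan, part III, analyses the whole sample for Aim 1: "The repeated-measures model will contain time, treatment, time-by-treatment interactions, and any covariates associated with weight loss", with further adjustment for change in physical activity. The Aim 2 models regress support provided and support received on treatment, "adjusted for the same covariates used in Aim 1". Part V adds an open list of control factors (age, BMI, SES, laboratory values, medication). Sample size according to F-test remarks that randomisation should make covariate adjustment unnecessary. None of these places names cohort as a model term, a subgroup or a consistency check.

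**The concern.** Cohort is a factor within which the arms are balanced, so the analysis would normally condition on it. Here it also marks calendar year, a largely separate peer group and a partly different app. If the cohorts differ in outcome and the model leaves cohort out, that difference goes into the residual variance, although the design has already removed it from the treatment comparison. The model standard error is then larger than the true sampling error.

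The plan also reports a single pooled points effect across two versions of the app, and nothing in it would show whether that effect was similar in both. Leaving cohort to the unnamed covariates makes its inclusion a choice made after the data are seen.

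**Working it through.** **1. Inputs.** From Statistical Design and Power: the aim is "to achieve 95% power (alpha = 0.05) for Aim 1", and for the method "we used an F-test on the interaction between time (two levels) and treatment arm (two levels) in a two-way ANOVA with repeated measurements". Effect size 0.1, correlation 0.7, evaluable N = 200, enrolled N = 240. The documents give no expected difference between cohorts, so the values of δ below are assumptions.

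**2. The plan's own figure.** For a 2 × 2 within-between interaction, λ = f² × N × m / (1 − ρ), with 1 and N − 2 degrees of freedom.
- With f = 0.1, m = 2, ρ = 0.7, N = 200: λ = 0.01 × 200 × 2 / 0.3 = 13.33, and power is 95.3%.
- The smallest even N reaching 95% is 198, which matches the stated 200.
- The match requires 0.1 to be Cohen's f. Read as Cohen's d, as the plan labels it (f = 0.05), the same formula needs N = 782. All power figures below take 0.1 as f.

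**3. Which cohort difference matters.** The Aim 1 test is time-by-treatment, which for participants with both weights is a comparison of weight change. A cohort difference in weight level cancels out of it, and only a difference in weight change matters. The useful Aim 1 term is therefore cohort-by-time; a cohort main effect alone does not act on the test. In Aim 2 the outcome is a single value per person, so the cohort main effect is the relevant term.

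**4. Cost of omission.** Take equal cohorts whose means differ by δ within-cohort SDs, with arms balanced in each. The residual variance is multiplied by 1 + δ²/4 and the model SE by its square root. The true sampling error of the contrast does not change. With √13.33 = 3.651, approximate Aim 1 power is Φ(3.651 − 1.96 × SE factor), and the true type I error is 2 × [1 − Φ(1.96 × SE factor)].

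| δ (assumed) | Variance factor | SE factor | Aim 1 power, N = 200 | True type I error |
|---|---|---|---|---|
| 0 | 1.000 | 1.000 | 95.5% | 5.0% |
| 0.3 | 1.0225 | 1.011 | 95.2% | 4.7% |
| 0.5 | 1.0625 | 1.031 | 94.9% | 4.3% |
| 0.8 | 1.160 | 1.077 | 93.8% | 3.5% |
| 1.0 | 1.250 | 1.118 | 92.8% | 2.8% |

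The first row is 95.5% rather than 95.3% because the table uses the normal approximation.

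**5. Cost of inclusion.** With one or two residual degrees of freedom removed, the exact formula still gives N = 198 for 95% power, and 95.3% power at N = 200.

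**6. What a by-cohort check can show.** With equal cohorts, the SE of the difference between the two cohort effects is twice the SE of the pooled effect. If that difference is as large as the whole planned effect, power is Φ(3.651/2 − 1.96) = 45% at N = 200. At N = 240, √(0.01 × 240 × 2 / 0.3) = 4.0, and power is Φ(4.0/2 − 1.96) = 52%. Within a single cohort, power for the planned effect is 72% with 100 evaluable participants and 80% with 120.

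**7. The response-limit dates.** If the limit ran for the whole of Cohort 1, it covers 50% of planned exposure, with equal cohorts followed for 52 weeks. If it was lifted at week 8 of Cohort 1, it covers 8/52 = 15.4% of that cohort and 7.7% of the trial. The other 44 weeks of Cohort 1 then ran under the Cohort 2 rule, and a cohort term does not separate the two reply rules.

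**The case against.** The strongest reply is that little is at risk. Both arms receive the same app apart from points, and arms are balanced within cohort, so pooling gives an unbiased contrast and leaving cohort out errs on the conservative side. This stands. A reader might infer from the change of app version that the pooled effect is biased; the allocation described in Randomization Procedure does not support that.

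Cohort could also enter the models without a change to the plan. A reader might infer that the one route is a test of association with weight loss. Part V does not bear this out: its list of control factors is open and not tied to weight loss. Neither route pre-specifies cohort, however, and that part of the concern remains.

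The link from the app changes to the outcomes can also be overstated:
- Unlimited replies might seem to raise the Aim 2 points total directly. Points are capped at one per activity and eight per day, so the ceiling does not move. Ratings of support received, and the number of days on which a reply is possible, could still change.
- Moving diet logging might seem to corrupt mLife activity data and the outreach prompts. The diet data were synchronised to mLife, and the documents do not say that inactivity is judged by where diet is logged.
- The ASA24 version also differs by cohort, but dietary recalls are not an outcome in either model.

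Finally, one might infer that points work under only one version of the app. If one cohort had half the planned effect or none, pooled power would be Φ(3.651 × 0.75 − 1.96) = 78% or Φ(3.651 × 0.5 − 1.96) = 45%. Nothing in the documents suggests such a difference, and a cohort term would not recover that power. The calculation shows why a consistency check is useful; it is not evidence that the effect varies.

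**Conclusion.** The omission is real and its consequences are modest. Cohort structures the allocation and coincides with documented differences in the app, yet it is not pre-specified in either model. The treatment contrast is unbiased. Model standard errors are about 1%, 3% and 8% too large if cohort means differ by 0.3, 0.5 and 0.8 SD. Even at 1 SD, Aim 1 power falls only to about 93%, and type I error stays below 5%. These figures rest on assumed differences, equal cohorts, balance within cohort and 0.1 taken as Cohen's f. For Aim 1 they apply to differences in weight change, not in weight level.

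The second gap is that no planned analysis looks at the points effect by cohort. Such a look can only be supportive, given 45% to 52% power for a difference as large as the planned effect.

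The two accounts of when the response limit was lifted do not agree as written, and the documents do not settle which is correct.

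**What to change.** In Analysis Plan, part III:

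1. Name cohort and cohort-by-time as fixed effects in the Aim 1 model, and cohort as a fixed effect in the Aim 2 models, whether or not cohort is associated with weight loss.
2. Report the treatment effect by cohort with confidence intervals, through cohort-by-time-by-treatment in Aim 1 and cohort-by-treatment in Aim 2. Label it a supportive consistency check with low power, and do not let it alter the primary conclusion.
3. Reconcile App Development and Use with Social support activities and gamification on when the response limit was lifted, and for which cohort. If it fell within Cohort 1, state that the cohort term does not separate the two reply rules. A before-and-after comparison within Cohort 1 is not a substitute, because it would be confounded with time on study.

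The cost is wording, two degrees of freedom in Aim 1 and one in Aim 2. Cohort is known for every participant, no new data are needed, and power at N = 200 stays about 95%.

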## **Overview of assessments**

Potential participants will be directed to a study website to learn more about the study and complete a screening questionnaire. If they qualify, they'll be invited to an orientation session where they'll learn more and sign a consent form. Participants will then complete online surveys measuring psychosocial variables and diet, and anthropometric data will be collected. Those who complete all baseline assessments will be randomly assigned to either the mLIFE+points or mLIFE group using a computer program allocation sequence, stratified by sex and baseline BMI (to ensure equal distribution of sex and weight classes among the two groups). All participants will complete assessments at baseline, 6, and 12 months. The study will involve two cohorts, each with 120 participants, staggered by 12 months.

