### **Sample size according to F-test**

Because our main outcomes will be measured at 12 months, we are using pilot work that collected weight loss outcomes at one year. Based on our pilot data (NETworks trial as this provides 12-month outcomes for weight), as well as several other one-year mHealth intervention studies, we calculated the sample size necessary to achieve 95% power (alpha = 0.05) for Aim 1 assuming a small effect size (Cohen's  $d = 0.1$ ) and an intra-cluster correlation (ICC) equal to 0.7. The sample size estimate was 200. For this calculation, we used an F-test on the interaction between time (two levels) and treatment arm (two levels) in a two-way ANOVA with repeated measurements (RM-ANOVA). We used a more conservative value of the ICC as compared to the actual estimate from the NETworks trial data (ICC = 0.9), as the latter would have resulted in a much smaller sample size (for a larger ICC, the residual sum of squares decreases, therefore precision increases and sample size decreases. The opposite is true when the test is strictly between subjects). Further, we assumed an attrition rate between 15 and 20%, and increased the sample size to 240. Thus, we aim to recruit a total of 240 participants (~120 per cohort), with the initial randomization assigning 120 to SocialPOD+points and 120 to SocialPOD-points.

Based on pilot study for overall app usage (Social POD  $50.7 \pm 25.0$  days and standard  $34.4 \pm 25.8$  days out of a possible 84 days) and points earned (mean of  $202 \pm 105$  points/participant with estimated 50 point difference between groups), our power for Aim 2 will be 99% for app usage and 95% for points earned based on our sample size from Aim 1.

We plan to use a random-effects (RE) model which is mathematically equivalent to repeated-measures-ANOVA. However, in the presence of loss to follow-up, RE models can handle responses that are missing at random. RE models can be adjusted for additional covariates if needed (though the randomization procedure should make this unnecessary). RE models provide additional information about the variance of the random effects which is valuable for understanding heterogeneity of responses and assessing the intra-cluster correlation (ICC).

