#### IV. Below details various types of bias and how our study aims to avoid them.

Type of Bias	How to Avoid
Pre-trial bias	
Flawed study design	We have a clearly defined risk and outcome and are using objective or validated methods. Standard operating procedures will be developed for data collection and assessors will be blinded to random assignment.
Selection bias	We will select participants using rigorous criteria to avoid confounding results. Participants will originate from the same general population. Because this is a well-designed, prospective study, selection bias should be avoided as outcome is unknown at time of enrollment.
Channeling bias	We will assign participants to study cohorts using rigorous criteria, stratifying by sex and race.
Bias during trial	
Interventionist bias	All study personnel interactions with participants will be standardized. As part of our treatment fidelity process, interactions with participants (e-mails, phone calls, etc.) will be regularly assessed and monitored to assure equal treatment among groups.
Recall bias	We will use objective data sources whenever possible. While surveys and the dietary recalls will rely on memory, these measures are currently the gold-standard way to assess these outcomes.
Transfer bias	We will carefully design plan for lost-to-follow-up participants prior to the start of the study. This will include number of contacts required after a participant does not attend classes or assessment visits.

Outcome Misclassification	We are using objective validated measures to assess all primary outcomes.
Bias after trial	
Citation bias	Our trial will be registered with clinicaltrials.gov prior to study recruitment for cohort 1. We will check registries for similar unpublished or in-progress trials prior to publication.
Confounding	Known confounders will be controlled during data analysis (such as medications). Unknown confounders will be controlled with randomization.

\* Adapted from Pannucci CJ, Wilkins EG. *Plast Reconstr Surg.* 2010 Aug; 126(2): 619–625.

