## V. Consideration of relevant biological variables

Of primary interest in the present study will be examining differences in outcomes by sex and age. Previous research has demonstrated that men lose more weight than women in behavioral weight loss interventions, but there is no indication that different weight loss strategies should be used. There is evidence that men may interact with technology, including health-related mobile technology, differently than women. For example, a study examining gender differences in usage of a physical activity app found that enjoyment and goal-setting were more important for women than men but that men more often shared their results and used the live tracking function in the app. Other research has found that men feel that mobile phone usage is more appropriate across a variety of social situations than women. In addition, those under 50 (and particularly those under 30) tend to have higher rates of smartphone ownership than those over 50. Based on these findings, we aim to conduct sub-analyses examining the impact of sex and age on social support provision and receipt and weight loss. We have been successful recruiting both men and AA participants in our previous studies and being situated in South Carolina and housing this work within the Prevention Research Center (where the current main research project is among AA churches in SC) will ensure we can consider both of these relevant biological variables. Our models will also control for other factors that could impact outcomes, including age, BMI, SES, baseline lab values, and medication use.

**A. Below details our approach to data management and validation, including our data management system, methods of data entry and cleaning, and event tracking and logistics**  
 [name], Project Manager, and [name], study PI, will develop and maintain the computerized data management system for this study. Use of the data management system will be restricted to only those persons having access authority.

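### The stratification factors should be named in the Aim 1 and Aim 2 models, and in Aim 1 a baseline covariate adjusts the test only if it has a time interaction

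*Combined protocol and SAP*

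**What the plan says.** **Randomisation.** The Randomization Procedure states: "A computerized blocks system, stratified by race (Black, Other) and sex, is used to ensure equal distribution among groups within each cohort". The bias table in Analysis Plan section IV agrees ("stratifying by sex and race"). The synopsis, under Overview of assessments, differs: "stratified by sex and baseline BMI". The Randomization Procedure is also not consistent on race. It first splits Black from all others, then builds separate lists for white and non-white participants.

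**Aim 1 model (Analysis Plan section III).** "Models will examine weight at baseline and at 12 months with a two-level time effect, two-level treatment effect, and two-way interaction between time and treatment". Then: "The repeated-measures model will contain time, treatment, time-by-treatment interactions, and any covariates associated with weight loss". Change in physical activity is added as a further covariate. The test is the time-by-treatment interaction at 0.05.

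**Aim 2 model (same section).** Support provided and support received are regressed on treatment group, with the Aim 1 covariates carried over.

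**Other statements on covariates.** The sample-size section says "RE models can be adjusted for additional covariates if needed (though the randomization procedure should make this unnecessary". Section V says "Our models will also control for other factors that could impact outcomes, including age, BMI, SES, baseline lab values, and medication use". The same section notes: "Previous research has demonstrated that men lose more weight than women in behavioral weight loss interventions".

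**The concern.** There are three linked gaps.

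1. The design balances the arms on sex and race within cohort, yet sex, race and cohort are not named terms in either primary model. When a factor that predicts the outcome has been balanced by design and is then left out of the model, the reported standard error of the treatment effect is too large. The test is conservative and some precision is wasted.
2. In Aim 1 the covariates are listed beside time, treatment and their interaction, with no covariate-by-time term. Read plainly, they are main effects. For a time-constant baseline covariate, that adjustment does nothing for the test the plan relies on. An analyst could follow the text faithfully and not notice.
3. The covariate clause has no candidate list, criterion or threshold. The sample-size section treats adjustment as optional, while section V says it will happen. The covariate set of the primary test is therefore not fixed in advance.

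**Working it through.** **1. Reproduce the plan's sample size.** Inputs from Sample size according to F-test: effect size 0.1, within-person correlation 0.7, alpha 0.05, power 95%, two arms, two times, N = 200. For the within-between interaction, the noncentrality is f² × N × m / (1 − ρ) = 0.01 × 200 × 2 / 0.3 = 13.33, with 1 and 198 degrees of freedom. Power at N = 200 is 95.3%, and the smallest N for 95% is 198. The stated 200 is reproduced if 0.1 is read as Cohen's f. The plan calls it d, which is a separate matter. The calculation contains no covariates.

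**2. Why a main effect cancels.** For participant i with treatment T and time-constant covariate x:
- baseline mean: a + δT + γx
- 12-month mean: a + τ + δT + θT + γx
- difference: τ + θT

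The term γx drops out, so with both weights observed the estimate of θ does not depend on x. If x also has a time interaction (coefficient κ), the difference becomes τ + θT + κx, and x does adjust the test.

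**3. Check by simulation.** Set-up: 240 participants randomised within sex-by-race strata, maximum likelihood with an unstructured 2×2 covariance, no treatment effect, 1000 trials per setting. Assumed inputs: 20% men, 35% in one race group, effects on weight change of 4 units (sex) and 3 units (race), residual SD 7. Variance explained = (16 × 0.16 + 9 × 0.2275) / (4.61 + 49) = 4.61 / 53.61, about 9%.

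| Mean model SE of time-by-treatment | No covariates | Main effects only | With time interactions |
|---|---|---|---|
| Complete data | 0.939 | 0.939 | 0.894 |
| About 20% dropout, related to sex and race | 1.050 | 1.051 | 1.000 |

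With complete data, main effects changed the estimate by at most 4 × 10⁻¹³. With dropout, they shifted it with an SD of 0.03 (at most 0.15) against an SE of 1.05, with no gain in mean precision. Only the time interactions shortened the SE, by about 5%.

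**4. Cost of omitting the stratifiers.** The documents give no value for the share R² of the variance of weight change that the stratifiers explain, so 2%, 5% and 10% are assumed. Under stratified randomisation, true SE = reported SE × √(1 − R²). Hence:
- excess of the reported SE: 1/√(1 − R²) − 1
- actual type I error: P(|Z| > 1.96/√(1 − R²))
- power unadjusted: Φ((√13.33 − 1.96)/√(1 − R²))
- power adjusted: Φ(√13.33/√(1 − R²) − 1.96)

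| R² | SE too large by | Actual type I error | Power unadjusted | Power adjusted |
|---|---|---|---|---|
| 2% | 1.0% | 4.8% | 95.6% | 95.8% |
| 5% | 2.6% | 4.4% | 95.9% | 96.3% |
| 10% | 5.4% | 3.9% | 96.3% | 97.1% |

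The power gain is 0.2 to 0.8 points. These are normal approximations.

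**5. Agreement of the two checks.** In the complete-data simulation, the unadjusted model SE was 0.939 against an empirical SD of 0.909, an excess of 3.3%. The formula gives 4.8% at R² = 9%. Simulated type I error was 4.9% (complete) and 4.7% (dropout), against 4.0% from the formula. The direction agrees, and the gap is within simulation error (about 0.7 points on the type I error). The model with time interactions gave 5.7% and 6.2%, using maximum-likelihood SEs and a 1.96 cut-off; restricted maximum likelihood with a t reference is the usual choice.

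**6. Laboratory values.** The Assessments table and the outcome list in Analysis Plan section I schedule no laboratory test. Later sections mention laboratory personnel and assessments, but no measurement is defined that could supply the covariate.

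**The case against.** Several points on the other side stand, and they limit the claim.

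- **Not every covariate is inert.** A reader might infer that no covariate entered as written can adjust the Aim 1 test. The documents do not support that. Medications and socioeconomic variables are collected at baseline, 6 and 12 months, and entered as time-varying they could move the interaction. The plan is also silent on functional form; main effects are the natural reading of its list, not a stated rule. In Aim 2, main effects do adjust the treatment comparison.
- **Selection on trial data is one reading.** A reader might infer that the plan commits to choosing covariates from the trial's own outcomes. It does not say so. Section V cites earlier research on sex, so sex could qualify beforehand. Its reference to controlling for other factors as well can be read as additional to sex and race. What stands is that the wording permits choice after the data are seen.
- **The stratifiers are in dispute.** On the synopsis version, BMI is a stratifier and section V does name it as a control. Sex is a stratifier in every version and is not in that list.
- **The top of the R² range is doubtful.** The passages considered here do not say that race predicts weight change. The block lists hold 3 × 5 + 5 × 4 = 35 places for men: 15% of 240 if that is the total, 29% of 120 if per cohort. For sex alone to explain 10%, the gap between men and women would have to be √(0.10/(0.146 × 0.854)) = 0.9 SD or √(0.10/(0.29 × 0.71)) = 0.7 SD of weight change.

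**Conclusion.** The point holds as a modest matter of precision and pre-specification. The models do not name the factors that the operative randomisation section uses. In Aim 1, a time-constant covariate without a time interaction leaves the test unchanged with complete data and essentially unchanged under the planned attrition. On the assumed R² of 2-10%, the loss is an SE about 1-5% too large and less than one point of power, starting from above 95%.

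A reader might infer that leaving out the stratifiers biases the result, inflates the type I error or undermines the sample size. Nothing here shows that: the error is on the conservative side, and 200 evaluable (240 enrolled) stands as far as this point goes. Beyond the assumed R², the size rests on the plan's own power inputs and on balance within strata, which attrition will loosen somewhat. The firmer reason to act is that the covariate set of the primary test is open.

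**What to change.** 1. Reconcile the synopsis with the Randomization Procedure, and the two codings of race within the latter, and state which factors the block lists actually used.
2. In Analysis Plan section III, replace the open-ended covariate clause with those factors (on the operative text: sex, race as coded in the lists, and cohort). Give each an interaction with time in the Aim 1 model and a main effect in the Aim 2 regressions.
3. Name any other baseline covariate that is kept before unblinding, and give it a time interaction in Aim 1. Bring the optional wording in the sample-size section into line.
4. Delete baseline laboratory values from section V.

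The adjustment for change in physical activity, which is measured after randomisation, is a separate question that this change does not settle.

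Cost: SAP wording and a few degrees of freedom. Sex and race are already collected, and cohort is known. Free improvement.
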